5.2.1.2 Additional analysis

For the analysis of cost-effectiveness, the total cost-effectiveness will be calculated as total health effect of the two strategies. The outcome of interest is the incremental cost-effectiveness ratio (ICER), which is defined by the incremental cost (ΔC = cost OT-led OA management – cost of rheumatologist-led OA management) per incremental QALY (ΔU = QALYs with OT-led OA – cost of rheumatologist-led OA). If the cost-per-QALY of the ICER is less than the cost-effectiveness acceptability threshold, the OT-led OA management may be considered a cost-effective alternative to the rheumatologist-led OA management. This criterion is usually summarised in the net-monetary benefit static:

(1) $NMB = W * \Delta U - \Delta C$, where W is the acceptability threshold value, and ΔU is the incremental utilities/QALYs gained and ΔC is the incremental cost. If the NMB is positive ($NMB > 0$), the new programme is considered to have acceptable cost-effectiveness for the decision maker, otherwise not.

As there is no current official acceptability threshold value (W), we will follow the approach of the Norwegian Medicines Agency (10) to calculate an absolute prognosis loss for the patients under the current treatment strategy. This static has been discussed in the official White Paper on priority setting and is often used as a proxy for the upper limit of willingness to pay per QALY, also known as the cost-effectiveness acceptability threshold.

Healthcare costs are a function of resource use and the unit cost of those resources. In this study, resource use is defined as the number and type of contact with healthcare personnel, administered treatment (such as injections or surgical interventions) and assistive devices, patient education and exercise options as well as work absence, taking a healthcare perspective. We will use official tariffs and rates as unit costs in valuing the resource use.

To calculate QALYs, we follow the recommended approach by the Norwegian Directorate of Health (11). The patients' description of their own health is taken from the collected EQ-5D data. These scores are subsequently weighted with preference weights from the general population. In the absence of a survival-effect from treatment, the calculated utility of health will serve as the measure of the QALY.

Finally, we will use non-parametric bootstrapping to assess the degree of uncertainty around the likelihood of cost-effectiveness (12). This allows assessing uncertainty without having to impose parametric assumptions on our highly skewed data. We will perform 10,000 bootstrap samples with replacement of the sample outcomes. For each bootstrapped sample replica, we calculated the net monetary benefit (1) using the assumed acceptability threshold (W). The likelihood of cost-effectiveness will then be calculated as the proportion of all bootstrapped samples in which OT-led OA management conferred a positive net monetary benefit.

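### SAP section 5.2.1.2 writes the QALY increment ΔU as QALYs minus a cost and contradicts its own description of ΔU under formula (1): a minor drafting error in a primary-objective formula

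*SAP*

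**What the plan says.** SAP section 5.2.1.2 makes the ICER the outcome of interest for cost-effectiveness. The cost increment is well formed: "ΔC = cost OT-led OA management – cost of rheumatologist-led OA management". The denominator is introduced with the words "per incremental QALY" and then written out as "ΔU = QALYs with OT-led OA – cost of rheumatologist-led OA".

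Two decision rules follow.

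- **ICER rule.** OT-led management may count as cost-effective on this condition: "If the cost-per-QALY of the ICER is less than the cost-effectiveness acceptability threshold".
- **NMB rule.** The same criterion is then summarised through formula (1), "NMB = W * \Delta U - \Delta C", with the note that "ΔU is the incremental utilities/QALYs gained and ΔC is the incremental cost". The rule reads: "If the NMB is positive ($NMB > 0$), the new programme is considered to have acceptable cost-effectiveness".

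Later in the section, formula (1) is evaluated in each of 10,000 bootstrap samples. The likelihood of cost-effectiveness is the share of samples with a positive NMB. The SAP gives no numerical value for W.

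**The concern.** The written ΔU has no coherent unit: a sum of money is taken from a number of QALYs. The section therefore describes ΔU in two incompatible ways, once as this mixed difference and once as a gain in QALYs.

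The formula is not background text. Cost-effectiveness is among the primary objectives in section 1.2.1 and the primary outcome definitions in section 5.1.2, and EQ-5D-5L stands at the primary level in section 5.1.4. ΔU is the denominator of the ICER and the term that W multiplies in formula (1), so it also enters every bootstrap replicate. A SAP should let a second analyst program such a quantity from the page, and here the only explicit subtraction is the faulty one.

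**Working it through.** The SAP states no ICER, NMB, cost, QALY or threshold figure, so there is nothing to reproduce. The check is algebra on its formulas, then numbers under labelled assumptions.

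**Notation.** C_OT and C_R are the costs, and Q_OT and Q_R the QALYs, of OT-led and rheumatologist-led care. ΔC = C_OT − C_R, as in the SAP.

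**Literal ICER.** With ΔU = Q_OT − C_R,

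ICER = (C_OT − C_R)/(Q_OT − C_R) = (C_R − C_OT)/(C_R − Q_OT).

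When C_R is far larger than Q_OT, this is about 1 − C_OT/C_R. Because C_OT cannot be below 0, it is at most C_R/(C_R − Q_OT). For C_R = 1,000 and Q_OT = 0.65 that bound is 1,000/999.35 = 1.00065. The ICER therefore falls below any W of realistic size, whatever the trial shows.

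**Literal NMB.** NMB = W(Q_OT − C_R) − (C_OT − C_R). It is positive only if C_R < (W·Q_OT − C_OT)/(W − 1). Take the case most favourable to OT-led care, C_OT = 0 and Q_OT = 1. At W = 275,000 the bound is 275,000/274,999 = 1.0000036. Rheumatologist-led care would have to cost about one currency unit or less.

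**Worked example.** Assumed: W = 275,000, C_R = 20,000, C_OT = 10,000, Q_R = 0.60, so ΔC = −10,000.

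| ΔU used | Q_OT | ΔU | ICER | ICER < W? | NMB | NMB > 0? |
|---|---|---|---|---|---|---|
| As written | 0.65 | 0.65 − 20,000 = −19,999.35 | −10,000/−19,999.35 = 0.50 | yes | 275,000 × (−19,999.35) + 10,000 = −5,499,811,250 | no |
| As written | 0.55 | 0.55 − 20,000 = −19,999.45 | −10,000/−19,999.45 = 0.50 | yes | 275,000 × (−19,999.45) + 10,000 = −5,499,838,750 | no |
| QALYs minus QALYs | 0.65 | 0.65 − 0.60 = 0.05 | −10,000/0.05 = −200,000 | yes | 275,000 × 0.05 + 10,000 = 23,750 | yes |
| QALYs minus QALYs | 0.55 | 0.55 − 0.60 = −0.05 | −10,000/−0.05 = 200,000 | yes | 275,000 × (−0.05) + 10,000 = −3,750 | no |

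**Range.** The assumed grid was W = 275,000 or 825,000, C_R = 1,000 or 20,000, C_OT/C_R = 0.5, 1.0 or 1.5, and Q_OT = 0.65 or 0.55 against Q_R = 0.60 (24 combinations).

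- With ΔU as written, the ICER is about 0.5, 0 or −0.5 and always below W. The NMB is always negative, from about −2.75 × 10^8 to −1.65 × 10^10. The two rules disagree in all 24.
- With ΔU as a QALY difference, the NMB runs from −51,250 to +51,250, and its sign follows the assumed data.

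**Source of the disagreement.** The literal ΔU is negative for any realistic cost, and dividing by a negative number reverses the inequality that links the ICER to W. The last row of the table shows the same reversal with a correct but negative ΔU. That is a property of the ICER rule as worded and separate from the slip in ΔU.

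**The case against.** The strongest reply is that nobody would be misled. The words just before the faulty expression call the quantity a QALY increment. Formula (1) carries its own, correct description of ΔU, and the bootstrap refers to formula (1). The parallel definition of ΔC supplies the form of the difference, and the section explains how QALYs come from the EQ-5D data. On this view one word was carried over from the ΔC definition, and only one sensible reading remains. In addition, the hypothesis test and decision rule in sections 2.4.1 and 2.4.3 concern response only, so no non-inferiority conclusion depends on ΔU.

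Most of this stands, and it settles the severity. It also disposes of two stronger readings that a reader might infer:

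- **That the ICER and NMB cannot be derived.** The documents do not support this. The intended ΔU can be recovered from the same section, and even the literal expressions can be computed, though they mean nothing.
- **That OT-led care could practically never be found cost-effective.** This holds only if the faulty expression is carried into the NMB, which is where the SAP describes ΔU correctly. Under the ICER rule the same expression would pass OT-led care practically always.

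What does not stand is the inference that no correction is needed. Neither correct description writes out the subtraction, and the one expression that does is wrong, in the denominator of the stated outcome of interest.

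**Conclusion.** The point holds as a minor error: a unit mistake and an internal contradiction in the definition of ΔU, with the intended meaning clear from context. Read literally, it would set the ICER rule and the NMB rule against each other whatever the data show.

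All costs, QALYs and values of W used here are assumptions, because the SAP gives none. The direction of the result does not depend on them, provided that rheumatologist-led care costs well over one currency unit per patient, W is far above 1, and QALYs over the follow-up are at most about 1. The billion-scale NMB values show only that the literal expression is meaningless. They do not forecast what the trial would report, since the risk that the analysis is run literally is low.

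**What to change.** In section 5.2.1.2, replace the written definition with: ΔU = QALYs with OT-led OA management − QALYs with rheumatologist-led OA management. State that this ΔU is used in the ICER, in formula (1) and in the bootstrap.

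The cost is one corrected expression in the SAP. Data collection, sample size and the non-inferiority analysis are unaffected. The correction does not make the two rules agree when ΔU is negative. While that line is being edited, a short clause could say that the NMB decides in that case.

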1.2 Trial Objectives

1.2.1 Primary Objective

The primary objectives of this study are to assess whether OT-led hand OA care is non-inferior to rheumatologist-led OA care with regards to the proportion of patients with disease improvement 6 months after the study visit, and whether OT-led hand OA care is more cost effective than rheumatologist-led care.

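### The ICER rule and the net monetary benefit rule are presented as one criterion, but they give opposite verdicts whenever OT-led care yields fewer QALYs

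*SAP*

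**What the plan says.** SAP section 1.2.1 includes among the primary objectives "whether OT-led hand OA care is more cost effective than rheumatologist-led care". Section 5.2.1.2 sets out how this will be judged, in four steps.

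- The headline measure: "The outcome of interest is the incremental cost-effectiveness ratio (ICER"), that is, incremental cost per incremental QALY, with both differences taken as OT-led minus rheumatologist-led care.
- A decision sentence for that measure: "If the cost-per-QALY of the ICER is less than the cost-effectiveness acceptability threshold, the OT-led OA management may be considered a cost-effective alternative".
- A bridge to a second measure: "This criterion is usually summarised in the net-monetary benefit static". This is NMB = W × ΔU − ΔC, where W is the acceptability threshold. If NMB is positive, "the new programme is considered to have acceptable cost-effectiveness for the decision maker, otherwise not".
- A bootstrap of 10,000 samples, in which the likelihood of cost-effectiveness is "the proportion of all bootstrapped samples in which OT-led OA management conferred a positive net monetary benefit".

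No part of the SAP says how to read the ICER when ΔU is negative or zero, or when one strategy dominates the other. The SAP gives no numeric value for W.

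The printed definition of the denominator is "ΔU = QALYs with OT-led OA – cost of rheumatologist-led OA", although the same section later says that "ΔU is the incremental utilities/QALYs gained".

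**The concern.** A ratio loses the signs of its parts. A negative ICER can mean cheaper and better, or dearer and worse. A positive ICER can mean paying more for a gain, or saving money at the price of a loss. Comparing the ICER with W is therefore a valid test only when ΔU is positive. The SAP states the comparison without that condition and then presents it as the same criterion as NMB > 0, which it is not.

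The case is a realistic one. The trial tests non-inferiority of OT-led care and is planned on equal response in the two arms (section 2.3). If QALYs are also about equal, the estimated ΔU can easily fall below zero by sampling variation alone. The same data would then support opposite verdicts on a primary objective, one from the ICER sentence and one from NMB and the bootstrap, and the SAP does not rank them.

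**Working it through.** **Inputs.** From section 5.2.1.2: ICER = ΔC/ΔU; rule A, cost-effective if ICER < W; rule B, cost-effective if NMB = W × ΔU − ΔC > 0. The SAP gives no expected costs, QALYs, standard errors or value of W, so there is no planned figure to reproduce. Every numeric input below is an assumption, in unspecified currency units. The sign result in step 1 depends on none of them.

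**Step 1: algebra.**

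- ΔU > 0: ΔC/ΔU < W ⇔ ΔC < W × ΔU ⇔ NMB > 0. The rules agree.
- ΔU < 0: ΔC/ΔU < W ⇔ ΔC > W × ΔU ⇔ NMB < 0. The rules are opposite.
- Exact tie (ICER = W, NMB = 0): neither rule is met. At ΔU = 0 the ICER is undefined, while NMB still gives an answer.

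A numerical check agrees. In 400,000 uniform draws (ΔU within ±0.1, ΔC within ±40,000) at each of W = 100,000, 200,000, 300,000, 500,000 and 1,000,000, the rules disagreed in 0% of draws in both quadrants with ΔU > 0 and in 100% in both quadrants with ΔU < 0.

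**Step 2: OT-led care dearer and less effective.** Assume ΔU = −0.02 and ΔC = +5,000. Then ICER = 5,000/(−0.02) = −250,000, below every positive W, so rule A passes. NMB = −0.02 × W − 5,000, so rule B fails. The last column is the probability that the NMB bootstrap would approximate, assuming normal, uncorrelated estimates with SEs of 0.015 (ΔU) and 3,000 (ΔC): SE(NMB) = √[(0.015 × W)² + 3,000²] and P(NMB > 0) = Φ(NMB/SE).

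| W | Rule A | NMB | Rule B | P(NMB > 0) |
|---|---|---|---|---|
| 100,000 | pass | −7,000 | fail | 1.8% |
| 200,000 | pass | −9,000 | fail | 1.7% |
| 300,000 | pass | −11,000 | fail | 2.1% |
| 500,000 | pass | −15,000 | fail | 3.2% |
| 1,000,000 | pass | −25,000 | fail | 5.1% |

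For example, at W = 300,000, SE = √(4,500² + 3,000²) = 5,408, −11,000/5,408 = −2.03, and P = 2.1%. Across SE pairs from 0.01/2,000 to 0.02/5,000 the range is 0.1% to 11.3%. The bootstrap would correctly count against OT-led care while the ICER sentence passes it.

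**Step 3: OT-led care cheaper and less effective.** Assume ΔU = −0.02 and ΔC = −5,000, so ICER = 250,000.

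- W = 200,000: NMB = −4,000 + 5,000 = +1,000, so rule B passes; 250,000 > W, so rule A fails.
- W = 300,000: NMB = −6,000 + 5,000 = −1,000, so rule B fails; 250,000 < W, so rule A passes.

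The ICER rule therefore errs in both directions.

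**Step 4: how often the rules could conflict.** This equals the chance that the estimated ΔU is negative. As an illustration, 10,000 normal draws of the estimates were taken with SD 0.015 for ΔU, mean −2,000 and SD 3,000 for ΔC, and W = 500,000.

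| Mean ΔU | Share with ΔU < 0 (rules conflict) | Share meeting NMB > 0 | Share meeting ICER < W |
|---|---|---|---|
| −0.01 | 74% | 36% | 86% |
| 0 | 49% | 60% | 86% |
| +0.01 | 25% | 81% | 90% |

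The share passing the NMB rule rises with the true QALY difference, as it should. The share passing the ICER rule hardly moves. The SAP does not plan to bootstrap the ICER rule; the table only shows how the two rules behave.

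**The case against.** The strongest reply is that the ICER sentence is introductory. It is permissive in tone, it leads straight into NMB, and the NMB rule is the definite two-sided one: a dominated strategy fails it outright. The only planned probability of cost-effectiveness uses NMB. On that reading, harm requires an analyst to compare a negative ICER with W and ignore the NMB from the same data. It stands that the NMB verdict and the bootstrap are correct as planned. It does not remove the problem: the ICER is the named outcome, it has its own pass rule, and nothing in the SAP says that NMB overrides it.

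A second reply is that the section describes ΔU in terms of QALYs gained, which could imply ΔU > 0. That phrase labels the quantity; it does not restrict its sign.

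Third, the 15-point margin concerns response, not QALYs, so it does not show that ΔU will be negative. That is fair. The case rests on sampling variation around a small or zero true difference, which needs no appeal to the margin.

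Fourth, sections 2.4.2 and 5.2.1.2 label cost-effectiveness an additional analysis, and the formal hypothesis test covers response only. No alpha-controlled claim is affected. Section 1.2.1 nevertheless places cost-effectiveness in the primary objective, and section 5.1.4 lists EQ-5D-5L at primary level.

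Finally, the numerical inputs are all assumed, and the 0% and 100% disagreement rates follow from the algebra by construction. Both points are true. The figures illustrate the contradiction and do not estimate how likely a wrong conclusion is in this trial.

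**Conclusion.** The concern holds. As written, the ICER sentence is a wrong decision rule for ΔU < 0, and the SAP wrongly equates it with NMB > 0. The two disagree for every negative ΔU apart from exact ties, at any W. The most serious consequence is that OT-led care that costs more and yields fewer QALYs meets the stated ICER criterion. This part rests on algebra alone; the sizes of NMB, the bootstrap probabilities and the frequency of conflict rest on the assumed inputs shown.

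The planned NMB calculation and bootstrap are unaffected, so this should be corrected before analysis but does not undermine the economic evaluation. The cost term in the printed ΔU is a separate editorial slip: the intended meaning is clear from later in the section, and it adds no weight to the main point.

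**What to change.** In section 5.2.1.2:

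1. Delete the sentence that compares the ICER with the threshold, or limit it explicitly to ΔU > 0.
2. State that NMB > 0, accompanied by the bootstrap probability already planned, is the sole decision rule.
3. Report the ICER descriptively, with ΔC, ΔU and the quadrant of the cost-effectiveness plane. Where one strategy is both cheaper and more effective, state dominance instead of a ratio.
4. Correct the definition to ΔU = QALYs with OT-led care − QALYs with rheumatologist-led care.

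Items 1, 2 and 4 remove the contradiction and the slip; item 3 is reporting practice that prevents the ratio from being misread. The cost is SAP wording only. The NMB formula and the 10,000 bootstrap samples are already in the plan, and no new data are needed.

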6.1 Adverse Events/Safety

The main considerations in this study relate to safety and non-inferiority. Since this study does not include novel interventions, we are not expecting any adverse events connected to the study design. We will therefore focus on the safety aspects of the two treatment approaches and evaluate them in

STATISTICAL ANALYSIS PLAN for TASKSHIFT

the health economics section of the analysis. For both groups the healthcare usage (including additional contact to healthcare professionals as well as supportive devices) related to hand OA between baseline and six months as well as twelve months will be registered, compared and used to evaluate cost-effectiveness.

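### Work absence is counted as resource use in a cost analysis that declares a healthcare perspective, so the incremental cost and everything built on it do not match the stated perspective

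*SAP*

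**What the plan says.** SAP section 1.2.1 places cost-effectiveness among the primary objectives: "whether OT-led hand OA care is more cost effective than rheumatologist-led care". Section 5.2.1.2 gives the method. Costs are built item by item: "Healthcare costs are a function of resource use and the unit cost of those resources". The items are contacts with healthcare personnel, administered treatments, assistive devices, and patient education and exercise options, followed by "as well as work absence, taking a healthcare perspective". Pricing is then stated for the whole list, with no item exempted: "We will use official tariffs and rates as unit costs in valuing the resource use".

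The resulting cost difference between arms, ΔC, enters the ICER and NMB = W × ΔU − ΔC, where ΔU is the QALY difference and W the acceptability threshold. If NMB is positive, "the new programme is considered to have acceptable cost-effectiveness for the decision maker, otherwise not". The probability of cost-effectiveness is "the proportion of all bootstrapped samples in which OT-led OA management conferred a positive net monetary benefit", from 10,000 resamples. The SAP nowhere sets work absence aside, leaves it unpriced, or plans a second analysis from another perspective.

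**The concern.** A costing perspective fixes whose costs count. A healthcare perspective covers resources used in delivering care. A day off work uses none of these. It is lost production, and it belongs in an extended or societal analysis. The sentence in section 5.2.1.2 therefore names a perspective and includes an item which that perspective leaves out.

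Two analysts could follow this SAP and compute different ΔC: one keeps absence because it is on the list, the other drops it because of the declared perspective. Each could claim compliance. If absence is kept, a result labelled as a healthcare answer contains another kind of cost, yet is not a full societal cost either. If the choice is left until costs by arm are known, it can be made, or appear to be made, in the light of the answer. What is at stake is the conclusion on one of the primary objectives.

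**Working it through.** The SAP gives no figure on this point to reproduce. There is no unit cost, no numerical W, no expected QALY difference and no absence data. The check is the algebra of the SAP's own rule, followed by an illustration on assumed figures.

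**1. Algebra.** Split the incremental cost (OT-led minus rheumatologist-led) as the list in section 5.2.1.2 implies:

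- ΔC = ΔC_health + ΔC_absence
- NMB_health = W × ΔU − ΔC_health
- NMB as written = W × ΔU − ΔC_health − ΔC_absence = NMB_health − ΔC_absence

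The sign of NMB changes when ΔC_absence has the same sign as NMB_health and exceeds it in absolute value. This holds in both directions.

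**2. Sign change in numbers (all assumed, arbitrary cost units, W = 100 per QALY).**

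- ΔU = 0.01, ΔC_health = 0: NMB_health = 100 × 0.01 − 0 = 1.0. If ΔC_absence = 1.5, NMB as written = 1.0 − 1.5 = −0.5.
- ΔU = −0.01, ΔC_health = 0: NMB_health = −1.0. If ΔC_absence = −1.5, NMB as written = −1.0 + 1.5 = 0.5.

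**3. Effect on the probability of cost-effectiveness (illustration).** From section 2.3: 200 per arm with 20% drop-out gives 200 × 0.80 = 160 per arm. Everything else is assumed:

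- ΔU = 0 without sampling error
- ΔC_health = −1 (OT-led care cheaper by one unit)
- SD of healthcare cost 6
- SD of absence 10 days over all patients
- absence independent of healthcare cost
- normal approximation in place of the bootstrap

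Formulas, with v the value of a day and d the mean extra absence days under OT-led care:

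- Healthcare only: SE = 6 × √(2/160) = 0.671, so P(NMB > 0) = Φ(1/0.671) = Φ(1.49) = 0.93.
- With absence: SE = √(0.671² + (10v)² × 2/160), and P(NMB > 0) = Φ((1 − v × d)/SE).
- Example, v = 1 and d = 0: SE = √(0.45 + 1.25) = 1.304, so P = Φ(0.767) = 0.78.

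| Extra absence days, OT-led (d) | v = 1 | v = 2 | v = 3 |
|---|---|---|---|
| 0 | 0.78 | 0.67 | 0.62 |
| 1 | 0.50 | 0.33 | 0.28 |
| 2 | 0.22 | 0.10 | 0.07 |

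The comparator for every cell is 0.93. The first row has no true difference in absence: the probability falls only because absence adds variance. These values show how the rule behaves. They do not predict this trial's result.

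**The case against.** **Absence may be recorded but not priced.** The costing paragraph opens by speaking of healthcare costs, and no method for valuing a lost working day is named. This is a fair reading of what may have been intended. As written, however, absence is inside the definition of resource use, and resource use is what gets valued. If it is not to be priced, the sentence needs correcting anyway.

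**The label, not the list, may be the mistake.** The SAP cannot settle this. It affects which correction is made, not whether one is needed.

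**The analysis is called additional.** Sections 2.4.2 and 5.2.1.2 carry that heading, and the only formal test and decision rule (sections 2.4.1 and 2.4.3) concern response. This limits the reach of the point. Section 1.2.1 nevertheless lists cost-effectiveness among the primary objectives.

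**Stronger readings that the SAP does not support.** A reader might infer that section 6.1 contradicts section 5.2.1.2, because it says: "For both groups the healthcare usage (including additional contact to healthcare professionals as well as supportive devices) related to hand OA" will be used to evaluate cost-effectiveness. But the wording is inclusive, the section concerns safety, and it also leaves out injections and surgery, which section 5.2.1.2 lists. It is not a complete cost list and does not exclude other inputs. A reader might also infer that absence costs will outweigh the saving from replacing a rheumatologist visit with an OT visit. The SAP gives neither visit cost, nor the share of patients at work, nor the frequency, distribution or value of absence. ΔC also covers much more than one visit.

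**Conclusion.** The inconsistency is real and lies within one sentence of section 5.2.1.2. Read literally, a productivity loss enters ΔC and so the ICER, the NMB rule and the bootstrap probability, all under a healthcare label. That the verdict can change sign follows from the SAP's own formula. Whether it would do so here, and by how much, cannot be computed from the document. The conclusion rests on one reading, that everything defined as resource use is priced, which is what the text says. It does not rest on section 6.1 or on any assumed cost. The non-inferiority analysis of response uses no cost data and is untouched.

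**What to change.** In section 5.2.1.2, remove work absence from base-case resource use, so that ΔC, the ICER, the NMB and the bootstrap probability are healthcare-perspective results, and base the cost-effectiveness conclusion on them. Add a second analysis, labelled as extended or societal perspective, that includes work absence and states how a day of absence is valued.

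If the sponsor wants the broader perspective as base case, change the perspective label instead, state the valuation method, and still report the healthcare-only result.

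Record the choice in the SAP before costs are compared by arm. The cost is a short edit to one paragraph and one extra run of an analysis already planned, with no new data. The small downside is two sets of cost results to present.

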2.6 Timing of Final Analysis

The main analysis is planned when all patients have concluded 182 days post baseline, all data have been entered, verified and validated and the primary database has been locked.

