5.1.1.15 QALY

Quality-adjusted life years, calculated based on scores in the utility measure EQ-5D-5L.

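### The EQ-5D utility is used as the QALY without multiplying by time, so the net monetary benefit is on the per-QALY scale only if the utility difference applies for about one year

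*SAP*

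**What the plan says.** SAP section 5.2.1.2 obtains utilities by applying general-population preference weights to patients' EQ-5D answers, citing a national guideline for QALYs. It then concludes: "In the absence of a survival-effect from treatment, the calculated utility of health will serve as the measure of the QALY".

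The net monetary benefit in the same section is NMB = W × ΔU − ΔC, where "ΔU is the incremental utilities/QALYs gained and ΔC is the incremental cost". W is to be set by way of a prognosis-loss calculation that is "often used as a proxy for the upper limit of willingness to pay per QALY". No value of W is given. The decision rule is NMB > 0, and the bootstrap reports "the proportion of all bootstrapped samples in which OT-led OA management conferred a positive net monetary benefit".

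On timing:
- Section 5.1.4 lists EQ-5D-5L at 182/364 days.
- Section 6.1 says that hand-OA healthcare use "between baseline and six months as well as twelve months will be registered, compared and used to evaluate cost-effectiveness".
- Section 2.6 says: "The main analysis is planned when all patients have concluded 182 days post baseline".
- Section 5.1.1.15 defines QALYs only as "Quality-adjusted life years, calculated based on scores in the utility measure EQ-5D-5L".

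No section states a time weight, or which of the two time points is the economic horizon.

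**The concern.** The inference in section 5.2.1.2 does not follow. Without a survival effect, length of life drops out of the comparison between arms, but the unit of time stays. A utility difference has no unit, whereas W is money per QALY, that is, per year in full health. Their product is on the right scale only if the utility difference applies for about one year. The slash between utilities and QALYs in the definition of ΔU repeats the equation of the two.

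ΔU enters the ICER, the NMB and the bootstrap probability of cost-effectiveness. Although section 5.2.1.2 is headed as an additional analysis, section 1.2.1 makes it a primary objective to assess "whether OT-led hand OA care is more cost effective than rheumatologist-led care". In a non-inferiority trial of task shifting, an OT arm that is cheaper and slightly less effective is a central scenario, and it is the one in which a scale error in ΔU can change the conclusion.

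**Working it through.** The SAP states no QALY, ICER, W or NMB figure, so there is nothing of its own to reproduce. The check is one of units.

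**Inputs.** Days 182 and 364 are from section 5.1.4. In years, 182/365.25 = 0.4983 and 364/365.25 = 0.9966. Let d be the size of the between-arm utility difference. The shape of the difference over time is an assumption, so several are shown.

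**Formulas.** QALY difference q = area under the utility-difference curve (trapezoid, years). Utility entered under the SAP's rule, read as a single end-of-horizon value, is u. Factor = u/q.

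| Horizon | Difference at the assessments | u | q | u/q |
|---|---|---|---|---|
| 6 months | d at days 0 and 182 | d | 0.4983d | 2.01 |
| 6 months | 0, d (linear) | d | 0.4983d/2 = 0.2491d | 4.01 |
| 12 months | d, d, d | d | 0.9966d | 1.00 |
| 12 months | 0, d, d | d | 0.2491d + 0.4983d = 0.7474d | 1.34 |
| 12 months | 0, d/2, d | d | 0.1246d + 0.3737d = 0.4983d | 2.01 |
| 12 months | 0, d, d/2 | 0.5d | 0.2491d + 0.3737d = 0.6229d | 0.80 |
| 12 months | 0, d, 0 | 0 | 0.4983d | 0 |

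**ICER.** Reported ΔC/u = (cost per QALY)/(factor). At 6 months the reported value is 1/2.007 = 50% to 1/4.014 = 25% of the cost per QALY.

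**Sign of the NMB.** Suppose OT-led care saves S and loses utility. As written, NMB = S − W|u|; by area, NMB = S − W|q|. The signs differ only when S lies between W|q| and W|u|.

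Illustration with assumed W = 300,000 and d = 0.02 (the SAP gives neither), so W × d = 6,000:

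- 6 months: signs differ for S of 2,990–6,000 (constant) or 1,495–6,000 (linear). At S = 3,500, NMB is 3,500 − 6,000 = −2,500 as written. By area it is 3,500 − 2,990 = +510 (constant) or 3,500 − 1,495 = +2,005 (linear).
- 12 months, overstated: practically no range for d, d, d; 4,485–6,000 for 0, d, d; 2,990–6,000 for 0, d/2, d.
- 12 months, understated: 3,000–3,737 for 0, d, d/2 (at S = 3,500, +500 as written and −237 by area); 0–2,990 for 0, d, 0 (at S = 2,000, +2,000 and −990).

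The bands scale with W. At 6 months, W = 200,000 gives 1,993–4,000 (constant) and 997–4,000 (linear); W = 800,000 gives 7,973–16,000 and 3,986–16,000.

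If one arm is both cheaper and better, and the utility difference keeps its direction throughout, the sign of the NMB does not change. Its size and the ICER can still be wrong.

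**The case against.** The best defence is that the criticised sentence is shorthand. The paragraph opens by adopting a national guideline for QALYs, the ICER is defined per incremental QALY, and section 5.1.2 refers to the protocol for a detailed description of the EQ-5D-5L score. On that reading the sentence means only that quality of life, and not its length, can differ between arms, and the time weighting is supplied elsewhere. Neither the guideline nor the protocol is at hand. Further, the SAP does not say that a single end-point utility is entered. With a 12-month horizon and time-averaged utility, the discrepancy is about 0.3%.

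Part of this stands. The size of the error is conditional, an unnamed horizon alone would be missing detail that the protocol may supply, and no mismatch between the cost and effect windows is claimed. But the SAP does more than stay silent: after citing the guideline it gives its own rule, and that rule has no time in it. An analyst who follows it applies no time weight. If the guideline or the protocol does weight by time, the SAP sentence contradicts it and needs correcting for that reason. The 12-month rescue needs either a horizon and an averaging rule that the SAP does not state, or a difference that is constant from day 0. The only analysis with a stated date is at day 182.

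**Conclusion.** The rule is wrong as written and should be corrected before the cost-effectiveness analysis is run. With day-182 utility and 6-month costs, it overstates the QALY difference 2.01-fold (constant difference) to 4.01-fold (linear from equal baselines). With day-364 utility and 12-month costs, the factor runs from 0 to 2.01 over the patterns examined and is 1.00 only for a difference constant from day 0. A wrong decision on NMB > 0 requires one arm to be cheaper but less effective, with the saving inside the bands shown; those bands rest on assumed W and d. The finding concerns the SAP text; what the cited guideline would add cannot be seen. The responder non-inferiority analysis is untouched.

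**What to change.** In section 5.2.1.2, replace the sentence that lets utility stand for the QALY with:

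> QALYs are computed per patient as the area under the EQ-5D-5L utility curve (trapezoid rule, time in years) over a stated horizon, and costs are counted over the same horizon.

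Name the primary horizon, 6 or 12 months, so that the choice is made before results are seen. In the definition of the net monetary benefit, let ΔU be incremental QALYs only and delete the alternative of utilities. If EQ-5D-5L was not collected at baseline, state the assumption for days 0 to 182 and vary it in a sensitivity analysis.

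The cost is two wording changes, one sentence naming the horizon and a few lines of code. Recruitment, visits and the responder analysis do not change.
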